In order to determine the effect of the FGID decision support module, we will complete the following study procedures: FGID module (data review): There is no contact with subjects for this portion of the study; this is a retrospective and prospective review of data. We will pull retrospective and prospective patient data from the EMR for FGID screening, diagnosis, and treatment in order to analyze module process and outcome data, including any difference in physician behavior at control vs. intervention clinics in the diagnosis, treatment, and symptom resolution of FGIDs. Control verses intervention clinic will be determined by cluster randomization at the clinic site level. A002: In order to determine the usability, "patient-friendliness" of this module, we will collect qualitative feedback about of the user's experience from a subset of 50 families who completed it. This one time questionnaire will be administered by REDCap survey. A003: Tool usability questionnaire: Expand enrollment aim to 50 to 100 participants. Survey (online and

phone): We will also conduct surveys with a subset of parents of patients and patients with a positive FGID screen to assess symptoms, parental concern, and parent satisfaction. With the parent's permission, patients ages 10-17 will also be invited to participate in the phone survey about their symptoms and satisfaction. The surveys will be conducted over various time points: approximately 1, 3, 6, and 12 months after the positive screen for a FGID. (We anticipate conducting surveys with a maximum of 600 parents/legal guardians and older patients.) Survey responses can be obtained from the parent, parent and child, or child only (age 10-17).

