Systematic Pediatric Assessment of Rome Criteria (SPARC)

Principal Investigator: [name] MD

IRB Protocol # 1811325201

NCT04773158

April 1, 2019

**Sample Size and Power Estimates.** We calculated our sample size using the binary primary outcome (whether there was resolution of symptoms of a FGID by Rome IV criteria in children and adolescents or whether parental reassurance was achieved for infants). We wish to detect a 15% difference between the control and intervention clinics in the rate of the primary outcome. Since each FGID has a different estimated background rate of improvement without intervention, we estimated an overall weighted average improvement rate. We also took into consideration of differences of prevalence of different FGID diagnosis. Therefore, based on the data presented in Table 3, we estimated an overall improvement rate of 30% for the control clinics. Though we do not anticipate much variability in this rate at our six study clinics, we will use six different rates in a wide range, 15%, 20%, 25%, 30%, 35% and 40%, at baseline in order to estimate intra-clinic correlation. This translates to an intra-class correlation coefficient 0.007. However, for a conservative estimation of sample size, we will use intra-class correlation 0.014, two times the intra-class correlation we estimated.

Table 3. Data Utilized for Sample Size Calculations				
FGID Diagnosis	Estimated Baseline Improvement in 3 months	Prevalence	Unique CHICA patients/yr in age group	Minimum Time Required
Infant regurgitation (0-12m)	25%	10%	3172	10 months
Infant dyschezia (0-9m)	25%	5%	2640	26 months
Infant colic (0-5m)	48% 	10%	1584	26 months
Cyclic vomiting syndrome (3m-18y)	70% 	5%	22544	4 months
Functional nausea/vomiting (8-18y)	50%	5%	9702	8 months
Functional dyspepsia (8-18y)	25%	10%	9702	4 months
Irritable bowel syndrome (8-18y)	37.5% 	15% 	9702	4 months
Abdominal migraine (8-18y)	20%	2% 	9702	16 months
Functional abdominal pain - NOS	20%	15%	9702	4 months
Functional constipation (0-18y)	20%	20%	23336	3 months

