Using a chi-square test and setting alpha at 0.05, the probability of detecting a statistically significant difference in the proportion of children with symptoms of any FGID with improvement in the primary outcome at 3 months from baseline between the intervention and the control group is 90%, with an effective sample size of 163 per group. Hence, the total effective sample size (n\*) is 326.

The unit of randomization is the clinic, but the unit of analysis is the individual patient. Since patients are nested within practice, responses from the patients within practice are likely to be

correlated. This intra-cluster correlation must be taken into account in the calculation of sample size and in the analyses. We computed the number of patients per clinic,  $m$ , required for the study, using the following equation:

$$m = \frac{1 - \rho}{\frac{k}{n^*} - \rho}$$

where  $\rho$  = intra-practice correlation  
 $k$  = number of clinics  
 $mk$  = total sample size  
 $n^*$  = total effective sample size =  $mk/DE$   
and  $DE$  = design effect =  $1 + \rho(m-1)$

Using 6 clinics and assuming intra-class correlation of 0.014, we need to recruit 224 families with a child between 0 and 18 per clinic. We anticipate that drop-out is not a major problem and unlikely to be more than 10% for the primary outcome. We will account for this factor by oversampling patients by 10%. According to the data presented in Table 3 and with an assumption that for each category of FGID diagnosis 50% of the patients will be in the control clinics and other 50% will be in intervention clinics, there will be about 5,500 patients/year/group with a FGID diagnosis. If we assume that only 66% of the parents will respond to the phone call at 3-month post baseline, we will have 3,630 patients/year/group. Therefore, the number of patients from which we are able to recruit is not a factor at all. We can have more than 90% power even to detect a 5% absolute difference with all available patients in one year.

**Data Analysis.** Baseline clinical and demographic data will be compared between the intervention and the control groups. Categorical variables will be examined using chi-square tests and continuous measures with Student's t-tests. The statistical analysis of the data will be performed using the SAS.

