**Primary Outcome Analysis:** The primary outcome is whether there was resolution of symptoms of a FGID by Rome IV criteria in children and adolescents or whether parental reassurance was achieved for infants. For this dichotomous outcome, we will use a non-linear mixed-effects model and will adjust for potential confounders (fixed effects) and clinic effects (random effects). To be specific, if  $Y_{ik}$  is a binary variable indicating whether the  $k^{\text{th}}$  patient in the  $i^{\text{th}}$  clinic was reported a resolution of FGID symptom, we have

$$\text{logit}(Y_{ik} = 1) = \alpha_i + \mathbf{X}_{ik}\beta, \text{ where } \alpha_i \sim N(0, \sigma^2).$$

The random component  $\alpha_i$  correlates outcomes of patients cared by the same clinic. Physicians would not be considered as a nesting factor since the same patients at different visits may not be seen by the same physician. The vector  $\mathbf{X}_{ik}$  represents fixed covariates and  $\beta$  represents the corresponding coefficients. The fixed covariates will include critical covariates such as treatment group, gender, and other patient and clinic level characteristics. We will also examine potential interaction terms among the covariates, particularly interactions between treatment arm and other covariates. If there is a significant treatment difference, we will report the 95% confidence interval of the treatment difference after adjusting for all confounding factors. The model will be fitted by the SAS procedure NL MIXED.

**Secondary Outcome Analyses:** The additional time points of 1, 6, and 12 months will be modeled identically to the primary outcome analysis. Furthermore, we will have a number of secondary outcomes which are count data aggregated within the 12 months after initial Rome IV

diagnosis. We will use Poisson regression to model these count data. To adjust for the possible differences between the intervention and control groups, we will use an approach similar to the analyses of primary outcomes and again clinic will be considered as a cluster factor to take into consideration the correlation in count data within each clinic. Family and provider satisfaction scores will be analyzed using Student's t-test, as well as a linear mixed-effects model as with other outcomes.

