Missing Data Analysis: We anticipate a low rate of missing data for the primary outcome since our CHICA system showed only 1.3% error rate due to omission of a data field. However, we anticipate a possible dropout rate of 10% for which we have adjusted the sample size. It is very unlikely that the dropout mechanism will depend on the unobserved outcome. Even if MNAR is true for certain subjects; given the low percentage of missing values, we think the bias induced is negligible. Under circumstances where compromise of power due to missing values is of concern, we will use a multiple imputation procedure to make use of all relevant observed data under the assumption that the data are Missing At Random (MAR). The SAS procedure MI and MIANALYZE will be used to implement the procedure.

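### The protocol's survey maximum of 600 people is not reconciled with the SAP's 1,344 families, and the passages on the source of the 3-month primary outcome conflict

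*Protocol*

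**What the plan says.** Protocol, section B, item q22123, plans online and phone surveys in a subset of screen-positive patients and their parents at about 1, 3, 6 and 12 months. The surveys cover symptoms, parental concern and satisfaction. On number: "We anticipate conducting surveys with a maximum of 600 parents/legal guardians and older patients". A response may come from a parent, a child aged 10 to 17, or both together.

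SAP, Sample Size and Power Estimates, states that "we need to recruit 224 families with a child between 0 and 18 per clinic", with six clinics. It then adds: "We will account for this factor by oversampling patients by 10" per cent. On clustering, "we will use intra-class correlation 0.014, two times the intra-class correlation we estimated". Its power statement is that the chance of detecting a difference "between the intervention and the control group is 90%, with an effective sample size of 163 per group".

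On where the 3-month outcome comes from, the text points in two directions:

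- **Survey.** The SAP counts available patients by assuming that 66% of "parents will respond to the phone call at 3-month post baseline". Under Secondary Outcome Analyses, "The additional time points of 1, 6, and 12 months will be modeled identically to the primary outcome analysis", which together with month 3 is the survey schedule.
- **Records.** Item q22123 also lists symptom resolution among the differences to be examined in the EMR data review. SAP, Missing Data Analysis, says: "We anticipate a low rate of missing data for the primary outcome since our CHICA system showed only 1.3% error rate".

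**The concern.** If the survey supplies the primary outcome, the protocol plans to collect fewer than half of the outcomes on which the SAP's sample size rests. A reader could not tell how many families the 3-month comparison will contain or what difference it can detect. If records supply the outcome, the survey maximum is irrelevant to the primary analysis, but the SAP's phone-response assumption is then out of place. Either way, the source and denominator of the primary outcome need to be fixed in writing before analysis.

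**Working it through.** **Inputs.** From the SAP: control rate 30%, difference 15 points (so 30% vs 45%), alpha 0.05, k = 6 clinics, ICC ρ = 0.014, total effective size n* = 326, 10% oversample. From the protocol: 600 people. Assumed: a two-sided test (the SAP does not say), equal clinic sizes, and the best case of one family per surveyed person.

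**1. The SAP's own figure.** m = (1 − ρ)/(k/n* − ρ) = 0.986/(6/326 − 0.014) = 223.84, so 224 per clinic. It reproduces. 6 × 224 = 1,344; × 1.1 = 1,478.4, so 1,479.

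**2. Size of the mismatch.** 600/1,344 = 45%; 600/1,479 = 41%.

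**3. Effective size.** Design effect DE = 1 + ρ(m − 1).
- 1,344 families: DE = 1 + 0.014 × 223 = 4.122; 1,344/4.122 = 326.1.
- 600 families: DE = 1 + 0.014 × 99 = 2.386; 600/2.386 = 251.5.

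**4. Power.** With n per group, p̄ = 0.375 and a pooled-variance normal approximation, power = Φ{[0.15√n − 1.96√(2p̄(1 − p̄))]/√(0.30 × 0.70 + 0.45 × 0.55)}.
- n = 163.0: (1.915 − 1.342)/0.676 = 0.848, power 80%.
- n = 125.7: (1.682 − 1.342)/0.676 = 0.503, power 69%.

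| Families with an outcome | DE | Effective n | Power | Detectable at 80% power |
|---|---|---|---|---|
| 1,344 | 4.122 | 326.1 | 80% | 15.0 points |
| 600 | 2.386 | 251.5 | 69% | 17.1 points |
| 540 (600 less 10%) | 2.246 | 240.4 | 67% | 17.5 points |
| 300 (two people from every family) | 1.686 | 177.9 | 54% | 20.5 points |

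The maximum costs about 11 points of power (0.802 − 0.692, before rounding).

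**5. Dependence on the ICC.** The SAP derives its ICC from six clinic rates of 15% to 40%. Their mean is 0.275 and their variance 0.0073. Dividing by 0.275 × 0.725 = 0.199 gives about 0.037; the SAP's 0.007 matches the variance before that division. At 0.037:
- 1,344 families: DE 9.251, effective n 145.3, power 46%.
- 600 families: DE 4.663, effective n 128.7, power 42%.

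The maximum then costs about 4 points, because clustering already limits both designs.

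**6. Which source fits.** Beyond the phone call and the matching schedule, the SAP speaks of families to recruit and expects 10% dropout; both suit a contacted sample better than a record review without contact. For infants the primary outcome is parental reassurance. The survey measures parental concern, while the data points listed for the module review (q725) name neither. The protocol attaches diagnosis-specific phone questionnaires, and no passage schedules a 3-month repeat of the clinic module. Against this stand the EMR and CHICA sentences. The phone-call sentence is itself a response-rate assumption, not an endpoint definition.

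All power figures use a normal approximation and ignore the small number of clinics.

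**The case against.** The strongest reply is that 600 need not bind. It is an anticipated maximum, not a sample-size calculation, and if the outcome is read from records the participant table's 10,000 children are the relevant pool. The SAP also says that availability is no constraint, with about 3,630 responders per year per group (66% of 5,500). The first part stands: the consequence is conditional on the survey being the source. The second does not remove the mismatch, because a large pool of eligible families does not raise the number the protocol plans to survey.

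The documents also differ in age. The SAP is dated April 2019 and is built around CHICA; the protocol is at amendment A017 and uses Epic. The SAP may simply not have been updated. That may explain the gap but does not close it.

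A reader might infer that the plan names no source at all for the 3-month outcome. That goes too far: the SAP ties its 3-month count to parents answering the phone call. The supportable point is that this text conflicts with the EMR and CHICA text. A reader might also attribute the whole fall from the stated 90% to 69% to the maximum. The figures do not support that either: 163 per group gives about 80% for 30% vs 45% whatever the survey size.

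**Conclusion.** The concern holds in conditional form. The two numbers are unreconciled, and the passages on the source of the primary outcome conflict, with the survey better supported. If the survey is the source, 600 is at most 45% of the SAP's number before oversampling, and power under the SAP's method is at most 69% rather than 80%. This rests on ICC 0.014, a two-sided 0.05 test, one family per person and the normal approximation. The 11-point loss should not be quoted without the ICC, since it shrinks to about 4 points at 0.037, where both sizes are below 50% power.

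It would be wrong to conclude that the primary analysis is certainly limited to 600, because the record-based reading is not excluded. The 90% claim at 163 per group is a separate error to be corrected in its own right. The plan should fix the present point before analysis; confidence is medium because the source is not settled.

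**What to change.** 1. State in the SAP that the 3-month survey supplies the primary outcome. If EMR data supply it instead, say so and state that 600 does not limit the primary analysis. In either case align protocol item q22123 with the SAP's sample-size and missing-data sections.
2. If it is the survey, put one target in both documents, counted as families with a 3-month outcome, and say how a parent and child of one family count towards 600.
3. If 600 stands, replace the SAP's 1,344 families and 90% power with what 600 delivers: at ICC 0.014, at most 69% power, or about 17 points detectable with 80% power. Give sensitivity to a larger ICC, such as the 0.037 implied by the SAP's clinic rates, and not to 0.007.

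**Cost.** Items 1 and 3 are mainly wording in the SAP, with a matching clarification in the protocol where its text must be aligned. Raising the maximum to 1,479 needs a protocol amendment. At up to $75 per full completer (25 + 3 × 10 + 20, one payment set per family assumed), it also needs up to (1,479 − 600) × 75 = $65,925 more in gift cards. Raising it would restore about 80% power at ICC 0.014, not 90%: effective n in six clinics cannot exceed 6/0.014 = 429, and 90% needs 434 (217 per group).

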Attachment Type

Data Collection Instrument

Attachment

FGID Algorithm Tool Usability and Qualitative Survey - Ages 0-13 - with SUS and demographics\_4.9.20 MF.docx

Name

Gastrointestinal Symptom Survey Tool – Usability and Qualitative Data Survey Ages 0 to 13 Years

Comments

Attachment Type

Data Collection Instrument

Attachment

FGID Algorithm Tool Usability and Qualitative Survey - Ages 14-17 - with SUS and demographics\_4.9.20 MF.docx

Name

Gastrointestinal Symptom Survey Tool – Usability and Qualitative Data Survey Ages 14 to 17 Years

Comments

Attachment Type

Data Collection Instrument

Attachment

FollowUpFunctionalDyspepsiaEpi.pdf

Name

Functional Dyspepsia- Epigastric Pain Syndrome Subtype 8yr to 18 yr Phone Survey

Draft

Comments

Attachment Type

Data Collection Instrument

Attachment

FollowUpIrritableBowelSyndrome.pdf

Name

Irritable Bowel Syndrome 8yr to 18 yr Phone Survey Draft

Comments

Attachment Type

Data Collection Instrument

Attachment

FollowUpAbdominalPainOtherwise.pdf

Name

Abdominal Pain-Otherwise not specified 8yr to 18 yr Phone Survey Draft

Comments

Attachment Type

Data Collection Instrument

Attachment

FollowUpAbdominalMigraine8yrTo.pdf

Name

Abdominal Migraine 8yr to 18 yr Phone Survey Draft

Comments

Attachment Type

Data Collection Instrument

Attachment

FollowUpInfantRegurgitation012-2.pdf

Name

Infant Regurgitation 0-12mo Phone Survey Draft

Comments

Attachment Type

Data Collection Instrument

Attachment

FollowUpInfantColic06mo\_System.pdf

Name

Infant Colic 0-6mo Phone Survey Draft

Comments

Attachment Type

Data Collection Instrument

Attachment

FollowUpInfantDyschezia012mont.pdf

Name

Infant Dyschezia 0-12months Phone Survey Draft

Comments

Attachment Type

Data Collection Instrument

Attachment

FollowUpAerophagiaAllAges0mo18.pdf

Name

Aerophagia all ages 0mo-18yrs Phone Survey Draft

Comments

Attachment Type

Data Collection Instrument

Attachment

FollowUpInfantRuminationSyndro.pdf

Name

Infant Rumination Syndrome 0-12mo Phone Survey Draft

Comments

Attachment Type  
Data Collection Instrument  
Attachment  
FollowUpRumination4yrsTo18yrs\_.pdf

Name  
Rumination 4yrs to 18yrs  
Comments

Attachment Type  
Data Collection Instrument  
Attachment  
FollowUpFunctionalConstipation.pdf  
Name  
Funct Constipation 0-12 mo Phone Survey Draft  
Comments

Attachment Type  
Data Collection Instrument  
Attachment  
FollowUpFunctionalConstipation.pdf  
Name  
Funct Constipation 12 mo to 18yrs Phone Survey Draft  
Comments

Attachment Type  
Data Collection Instrument  
Attachment  
FollowUpCyclicVomitingSyndrome-2.pdf  
Name  
Cyclic Vomiting Syn 0-18yrs Phone Survey Draft  
Comments

Attachment Type  
Data Collection Instrument  
Attachment  
FollowUpFunctionalDiarrhea6moT.pdf  
Name  
Functional Diarrhea 6mo to 8 yrs Phone Survey Draft  
Comments

Attachment Type  
Data Collection Instrument

Attachment

FollowUpNonRetentiveFecallIncon.pdf

Name

Non Retentive Fecal Incontinence 4yr to 18 yr Phone Survey Draft

Comments

Attachment Type

Data Collection Instrument

Attachment

FollowUpFunctionalVomiting8yrT.pdf

Name

Functional Vomiting 8yr to 18 yr Phone Survey Draft

Comments

Attachment Type

Data Collection Instrument

Attachment

FollowUpFunctionalNausea8yrTo1.pdf

Name

Functional Nausea 8yr to 18 yr Phone Survey Draft

Comments

Attachment Type

Data Collection Instrument

Attachment

FollowUpFunctionalDyspepsiaPos.pdf

Name

Functional Dyspepsia- Postprandial Distress Subtype 8yr to 18 yr Phone Survey Draft

Comments

Attachment Type

Other

Attachment

MyChart%20Msg\_FGID%20module%20pilot\_6.11.20.docx

Name

MyChart script (for batch messaging) to patient introduce FGID module for pilot testing

Comments

Attachment Type

Recruitment Materials

Attachment

SIS Usability Questionnaire \_recruitment Intro\_4.17.20.docx

Name

Introduction to SIS For Tool Usability Survey (questionnaire)

Comments

A002: Version 1.27.20 A003:4.17.20 Draft of email communication to introduce SIS for tool usability questionnaire.

Attachment Type

Recruitment Materials

Attachment

A012\_MyChart Intro to Phone Surveys.docx

Name

Phone Survey Recruitment: MyChart Introduction

Comments

A012 replaced A008 version

Attachment Type

Recruitment Materials

Attachment

A014\_Verbal Intro \_Phone Contact\_Parent\_Patient.docx

Name

Phone Surveys PResNet Intro Script

Comments

Replaces: A011\_Verbal Intro \_Phone Contact\_Parent\_Patient.docx

Attachment Type

Study Information Sheet

Attachment

1811325201A002\_SIS Usability survey\_\_4.17.20 .docx

Name

SIS for Tool Usability Survey

Comments

A002: Version 1.27.20 A003: Version 4.17.20

Attachment Type

Study Information Sheet

Attachment

1811325201A014 - [name] - SIS and Auth Phone or Online Survey - Oct 2023.docx

Name

Phone Survey SIS

Comments

A011: Version 2.15.23 A012: Version 5.30.23 A013: Version 7.18.2023

Attachment Type

Recruitment Materials

Attachment

A011\_Email Script\_Phone Survey Recruitment.docx

Name

Comments

A014: Cease use of this document. With updated requirements, will not send email communication to potential participants without attaining their consent to send.

Attachment Type

Recruitment Materials

Attachment

A012.1\_MyChart Intro to Phone Surveys-1\_Spanish rev.docx

Name

Comments

replaced A008 version

Attachment Type

Recruitment Materials

Attachment

A014\_Verbal Intro \_Phone Contact\_Parent\_Patient\_Spanish rev.docx

Name

Comments

Replaces: A011\_Verbal Intro \_Phone Contact\_Parent\_Patient\_Spanish rev.docx

Attachment Type

Study Information Sheet

Attachment

1811325201A014- [name] - SIS and Auth Phone Survey - Oct 2023\_Spanish rev-2.docx

Name

Phone Survey SIS - Spanish

Comments

Attachment Type

Recruitment Materials

Attachment

A011\_Email Script\_Phone Survey Recruitment\_Spanish rev.docx

Name

Comments

A014: Cease use of this document. With updated requirements, will not send email communication to potential participants without attaining their consent to send.

Attachment Type

Other

Attachment

A015- Draft E-Consent.docx

Name

Comments

New: For the online enrollment of survey participants. Same language as SIS/Auth placed in RC E-consent framework. A015 replaced A013.

Attachment Type

Other

